Over 200,000 *in vitro* fertilization (IVF) cycles were initiated in the United States in 2015,¹ allowing thousands of infertile couples to start families. Although most of the steps in IVF protocols are based on strong evidence, one, prophylactic antibiotic administration, is commonplace but not proven to produce benefit. This practice began in 1978 as a means to prevent bacterial contamination of the tip of the catheter used to transfer embryos into the uterus.² Although subsequent studies showed that bacterial contamination of the transfer catheters had a negative impact on IVF cycle outcomes,^{3,4} a more recent, robust randomized controlled trial powered to detect catheter tip contamination rates noted a decrease in contamination with routine administration of amoxicillin-clavulanate but no difference in clinical pregnancy rate.⁵ Current standard of care in our practice for a fresh IVF cycle is to administer one dose of 1 gram oral azithromycin (to both male and female partners) on day one of the IVF cycle start. Given the limited evidence for benefit and the true risk for subjecting patients to unnecessary treatments, we must determine whether prophylactic antibiotics actually improve the IVF outcome that matters most to couples: pregnancy.

A2 Primary Hypothesis

Our hypothesis is that withholding antibiotic prophylaxis will be non-inferior to routine administration.

A3 Purpose of the Study Protocol

The objective of this study protocol is to determine the impact on clinical pregnancy rate of withholding routine prophylactic antibiotic therapy during IVF.

As a smaller exploratory study within our RCT we aim to assess alterations and influence of the vaginal microbiome of women going through a fresh IVF cycles with a mid-vaginal swab at three time points in 50 women (25 in each arm): at the time of baseline testing, prior to egg retrieval and at the time of embryo transfer. Lastly we plan to obtain a swab at the time of embryo transfer to assess the human virome, which has never been described or evaluated in the IVF population.^{6,7} We will correlate our findings with the clinical outcomes we plan to track as a part of our primary study. We will consent and enroll the first 50 couples (25 in each arm) going through their first IVF cycle who enroll in the PAPET trial for the microbiome/virome study as well. The male partners of the women enrolled in the pilot RCT will also be enrolled in the pilot RCT. A small volume of the sample they produce at the time of *in vitro* fertilization will be obtained to evaluate the microbiome and virome in them in the same fashion.

B Background

B1 Prior Literature and Studies

Limited evidence supporting a common IVF practice: Although patients are routinely prescribed prophylactic antibiotics during an IVF cycle to improve embryo transfer success rates, little evidence supports this practice. A 2012 Cochrane review analyzed randomized controlled trials from the literature but only identified one study that was suitable for inclusion.⁸ In that trial, 350 women were randomized to receive either prophylactic amoxicillin and clavulanic acid on the day before and the day of embryo transfer, or no antibiotic treatment.⁵ The primary and secondary outcomes were catheter contamination rate and clinical pregnancy rate, respectively. Although the catheter contamination rate was significantly lower in the antibiotic group than in the control group (49.4% versus 62.3%, $P<0.03$), there was no difference in clinical pregnancy rate (36% versus 35.5% respectively, $P=0.83$). Impact on live birth rate was not assessed. A more recent retrospective analysis of 876 embryo transfers assessed the impact of discontinuation of routine corticosteroid and antibiotic administration during IVF cycles and found no significant difference in clinical pregnancy rate (56.1% in medicated group versus 61.5% in un-medicated group, $P=0.10$) or other secondary outcomes including clinical miscarriage and live birth rate.⁹ Given this limited evidence about the clinical usefulness of prophylactic antibiotics, a summary statement on embryo transfer from the American Society for Reproductive Medicine states that, “a recommendation for routine prophylactic antibiotics cannot be made”.¹⁰ Thus, we need a well-designed randomized controlled study to rigorously address this question and inform recommendations for the thousands of IVF cycles completed each year.

Potential of prophylactic antibiotics to cause harm: The impact of broad-spectrum antibiotic exposure in the preconception period is not well described but could have the unintended outcome of altering the follicular and endometrial microbiome, which may play a significant role in reproductive competence and IVF outcomes.^{11,12} For example, a prospective study of 35 infertile patients undergoing IVF demonstrated that a *Lactobacillus*-dominated endometrial environment was associated with higher rates of implantation (60.7% vs. 23.1%, $P=0.02$), pregnancy (70.6% vs. 33.3%, $P=0.03$), ongoing pregnancy (58.8% vs. 13.3%, $P=0.02$) and live birth (58.8% vs. 6.7%, $P=0.002$).¹³ Vaginal microbiota diversity has also been implicated as a causative factor in preterm delivery which is known to occur with higher incidence in the IVF population.^{1,14} The microbial community structure of the vagina and endometrium could be negatively affected by potentially unnecessary broad-spectrum antibiotic exposure. We intend to provide proof of concept with our smaller exploratory study evaluating the vaginal and endometrial microbiome and changed across an IVF cycle and as a result of prophylactic antibiotic exposure. Additionally, the *critical* importance of avoiding the misuse and overuse of antibiotics is continually discussed across all fields of medicine because of the increasing incidence of widespread antibiotic resistance.¹⁵⁻¹⁷ Finally, most antibiotics cause negative side effects including nausea, emesis, and yeast vaginitis and may add unneeded stress in the already-complicated IVF treatment process.

B2 Rationale for this Study

Non-inferiority RCT:

Current standard of care in our practice for a fresh IVF cycle is to administer one dose of 1 gram oral azithromycin (to both male and female partners) on day one of the IVF cycle start. This practice is of unproven clinical benefit and is based on theoretical risk and dated, poor-quality data.^{2-5,8,9} Although prophylactic antibiotic treatment may

decrease contamination of the embryo transfer catheter tip, no studies have been powered to determine impact on clinical pregnancy rate, the most direct correlate with successful IVF outcome.² This will be the first randomized controlled trial powered to detect a difference in the primary endpoint of clinical pregnancy rate.

Exploratory Pilot Study:

Profiling the vaginal and seminal microbiome and human virome in a smaller cohort of patients going through their first IVF cycle is an exploratory portion of this study. Existing studies are limited and conflicting regarding influence of the microbiome on IVF cycle outcomes.¹¹⁻¹³ This would be the first study to evaluate alterations in the reproductive tract microbiome across the IVF cycle in response to medications and supraphysiologic hormone levels, and the first to evaluate the human virome in this patient population.^{6,7} We would examine differences within and between groups and assess for the potential impact and association clinical outcomes of those patients exposed to prophylactic azithromycin, and those who are not. Optimizing the vaginal microbiome could serve as a potential target for therapy to help increase IVF success rates in the future with the goal of a full term, live birth.

C Study Objectives

C1 Primary Aim

Specific Aim 1: Determine the effect of withholding prophylactic antibiotic administration on clinical pregnancy rate (defined as a gestational sac, with fetal pole and cardiac activity, on ultrasound).

We *hypothesize* that withholding prophylactic antibiotics before embryo transfer will be non-inferior (absolute difference $\leq 15\%$) to routine prophylaxis in terms of clinical pregnancy rates.

C2 Secondary Aim

Specific Aim 2: Evaluate the impact of prophylactic antibiotic administration on miscarriage rate (pregnancy loss per clinical pregnancy) before 20 weeks.

Our *working hypothesis* is that miscarriage rates will be equivalent between the two groups.

Specific Aim 3: Determine the effect of no prophylactic antibiotic administration on embryo development.

We *hypothesize* that embryo development, as evaluated by fertilization rate (number of two-pronuclei embryos per mature oocyte), blastocyst conversion rate (number of day 5 embryos from two-pronuclei embryos), and blastocyst utilization rate (number of day 5 embryos transferred or frozen per two-pronuclei embryos) will be equivalent between the two groups.

Specific Aim 4: Determine the impact of prophylactic antibiotics or withholding prophylaxis on the vaginal and endometrial microbiome.

We *hypothesize* that azithromycin will impact the vaginal microbiome. Additionally, we expect to see changes across the IVF cycle that may be associated with cycle outcome endpoints.

Specific Aim 5: Evaluate the implications of the human virome on IVF outcomes.

We *hypothesize* that subclinical eukaryotic viruses will be associated with negative IVF cycle outcomes.

C3 Rationale for the Selection of Outcome Measures

We expect to define the clinical impact of withholding antibiotic prophylaxis before embryo transfer as measured by markers of a successful IVF cycle. As we hypothesize that withholding prophylaxis will be non-inferior to routine antibiotic administration, these results are expected have a positive clinical impact by decreasing unnecessary broad-spectrum antibiotic exposure and potentially creating a paradigm shift in IVF protocols.

D Study Design

D1 Overview or Design Summary

This will be a prospective randomized controlled non-inferiority trial in which 178 couples will receive the standard of care prophylactic antibiotics (control) and 178 will not receive prophylactic antibiotics (experimental). The primary outcome is clinical pregnancy rate. The expected primary outcome is that withholding prophylactic antibiotics will be non-inferior to antibiotic prophylaxis in terms of clinical pregnancy rate. Secondary outcomes include spontaneous miscarriage rate and embryo development as measured by fertilization rate, blastocyst conversion rate, blastocyst utilization rate, and live birth rate.

D2 Subject Selection and Withdrawal

2.a Inclusion Criteria

The female partner must be aged 18–43 years and going through a fresh IVF cycle. The male partner must be aged 18 at minimum. There is no upper age limit to males.

2.a Exclusion Criteria

Couples will be excluded from enrollment if they have any contraindication to antibiotic treatment (ie: allergy), are not intending to undergo embryo transfer (fertility preservation patients and oocyte donors), require use of extended antibiotic coverage at time of egg retrieval, are already on antibiotics for any reason (e.g., upper respiratory infection), have a recent history of pelvic infection, or are planning on limited insemination (inseminating a limited number of the eggs retrieved).

2.b Ethical Considerations

Participation will be completely voluntary. Patients care will not be impacted in any way by their decision to participate or lack thereof. Incidence of pelvic infection following embryo transfer approaches zero in this low risk population therefore patients are not being placed at any additional undo risk. They may be spared from experiencing potential adverse side effects of the oral antibiotic.

2.c Subject Recruitment Plans and Consent Process

Couples going through fresh IVF cycles will be identified and their charts reviewed to assess eligibility for inclusion. Eligible couples will be contacted via phone by a trained study coordinator and offered enrollment. Those who express interest will have a time arranged for both partners to provide written consent in the office. If the patient or couple is unable to find a mutually convenient time to come into the office for consent, both the patient and their partner will be emailed the consent form for review. They will then be consented in full over the phone and given instruction on return of the hard copy of the signed consents. Couples will not be randomized until receipt of the hard copy of their signed consents and review and signature of the research team member providing consent. Couples will only be included in the study during one IVF cycle. Subjects going through their first IVF cycle will also have an introduction to the study during IVF orientation.

2.d Randomization Method and Blinding

Couples will be randomized after providing written consent. Written consent will be obtained separately for both the male and female partner. In the case of same sex couples, only the female undergoing embryo transfer will be consented. Fifty couples going through their first IVF cycle enrolled in the noninferiority trial will also be offered enrollment in the pilot RCT and subsequently consented for the microbiome and virome profiling exploratory study. After consent, randomization in a 1:1 ratio to prophylactic antibiotics or no antibiotics will be performed in a block-randomized fashion per cycle number via computer random number generator. Couples randomized to the antibiotic group will receive the current standard regimen in our clinic: 1 gram azithromycin oral once for both partners the day controlled ovarian stimulation is initiated with injectable gonadotropins (IVF cycle start). In cases of same-sex couples, only the female undergoing the embryo transfer receives prophylaxis. Couples randomized to the no-antibiotic treatment group will not be prescribed oral antibiotic prophylaxis. Couples who agree to participate will have their charts marked indicating participation in the study. The couples' respective nurses will receive a message that will remain part of the electronic medical record regarding patient treatment group allocation so they can prescribe antibiotics appropriately. Embryologists who assess the embryo outcome measures will be blinded to patient treatment group allocation. The patients and their providers and nurses will not be blinded to treatment group allocation.

2.e Risks and Benefits

Potential problems with our study may be insufficient patient recruitment. The process of IVF is already stressful, time and user intensive and we will have to consent both

partners. Patients may be hesitant to deviate from our previous standard of care. On the other hand, patients may want to avoid additional medication and may not take the antibiotic regardless to which arm they are randomized. We would mitigate this risk by a thorough informed consent and expressing our goal is to improve our current IVF protocols and that the best approach is not known while emphasizing the importance of compliance. Reportable severe events include development of pelvic infection following embryo transfer, a significant increase in spontaneous miscarriage rates or a note in increased contamination rates in the lab. Risks of pelvic infection in this low risk population following embryo transfer is remarkably rare as stated above and we do not anticipate this occurring. We anticipate miscarriage rates to be equivalent or improved in the non-prophylaxis group. The lab uses genatmicin routinely in embryo culture media to decrease contamination rates and will continue to be closely monitored for any increase in contamination rates. Reportable non-severe adverse events include yeast vaginitis, nausea and vomiting or other adverse reactions from antibiotic prophylaxis.

Obtaining a mid-vaginal swab poses little to no risk to the patient. The patient may experience some slight discomfort from one additional speculum exam at the time of baseline testing. The embryo transfer catheter tip will be sequenced for comparison to the vaginal swab following embryo transfer and will require no additional invasive testing or exams.

2.f Early Withdrawal of Subjects

While loss to follow up is extremely rare in this circumstance, some patients who are enrolled and randomized may not make it to egg retrieval or may not get an embryo transfer due to either a poor response to medications or poor embryo quality. We will account for these patients in our 5% drop out estimation and they will not be included in analysis.

2.g When and How to Withdraw Subjects

Patients can withdraw from the study at any time if they choose to do so. Their care will not be impacted by their participation or lack thereof.

2.h Data Collection and Follow-up for Withdrawn Subjects

Subjects who withdraw will not be included in the final data analysis.

D3 Study Drug –

3.a Description

Azithromycin is routinely given to both partners (in male/female couples) or to the embryo recipient in same sex couples or gestational carriers when they start their IVF cycle medications and is our current standard of care.

3.b Treatment Regimen

1 gram oral azithromycin, once the day of IVF cycle start (when they start injectable gonadotropin medications) which is our current standard of care.

3.c Method for Assigning Subjects to Treatment Groups

Computer random number generator.

3.d Preparation and Administration of Study Drug

Azithromycine will be prepared and dispensed by the patients preferred pharmacy as is standard practice if they are randomized to the antibiotic prophylaxis group.

3.e Subject Compliance Monitoring

Patients will give verbal confirmation of compliance.

3.f Blinding of Study Drug

Patients will not be blinded to which group they're in. A placebo control will not be used.

3.g Receiving, Storage, Dispensing and Return

Azithromycin will be prepared and dispensed by the patients preferred pharmacy as is standard practice if they are randomized to the antibiotic prophylaxis group.

E Study Procedures

E1 Screening for Eligibility

Couples will be screened for eligibility by their primary physician, the primary investigator, [name] or the Research Project Coordinator. If they meet the inclusion and exclusion criteria they will be offered enrollment.

E2 Schedule of Measurements

Outcomes measures are routinely tracked by our clinical to report to the Society of Assisted Reproductive Technology (SART). Patients who participate in the study will not be required to make any additional visits beyond consent.

E3 Visit 1

Outcome measures for specific aim 3 will be tracked from the patients initial oocyte retrieval and embryo transfer visit. The lab routinely tracks this data and no additional query or visits will be required in term of embryo development data.

E4 Visit 2 etc.

Specific Aim 1 will be addressed and tracked when patients come in for their viability ultrasound at 6-7 weeks gestation which is routine practice in our clinic. Clinical pregnancy is defined as a gestational sac, with fetal pole and cardiac activity, on

ultrasound. No additional visits will be required. Patients will continue to be tracked once they are released from our practice to their primary OBGYN to track miscarriage rate (spontaneous loss prior to 20 weeks) and subsequent live birth outcomes.

Schedule of Visits for Microbiome/Virome Study:

Outcome measures will be assessed the same as th above aforementioned schedule of measurements for the noninferiority trial. Collection of specimens for the exploratory study will occur as described below:

Visit 1-

Women enrolled in the smaller exploratory study will have a midvaginal swab obtained when they get their baseline testing prior to ultrasound. This visit is already required in the IVF cycle and will not require an additional visit to collect the specimen.

Visit 2-

The second specimen will be obtained with a midvaginal swab prior to egg retrieval. This visit is already required in the IVF cycle and will not require an additional visit to collect the specimen.

Visit 3-

The third and final specimen will be obtained via midvaginal swab prior to embryo transfer. This visit is already required in the IVF cycle and will not require an additional visit to collect the specimen. When the male partner produces a sample for use for IVF at this time, a 100 microliter volume will be obtained and frozen separately. No additional visit will be required for them.

All specimen swabs collected for microbiome and virome profiling will be flash frozen at -80 celsius until all specimens have been collected and can be batch analyzed at the same time.

E5 Safety and Adverse Events

5.a Safety and Compliance Monitoring

As administration of 1 gram oral Azithromycin is standard of care in our practice no additional risk will be incurred from prescribing the antibiotic prophylaxis. Patients will be asked regarding compliance with medication administration and if any adverse side effects were incurred including yeast vaginitis, nausea and vomiting or other adverse reactions from antibiotic prophylaxis.

5.b Medical Monitoring

i Institutional Data and Safety Monitoring Board

In addition to principle investigator review of adverse events, a data and safety monitoring board (DSMB) will be established. This will include [name], [name], PhD, [name], MSCI and [name] and [name]. The designated group will meet once enrollment reaches 50% and then every 6 months thereafter to review occurrence of adverse events in addition to assessing recruitment progress and will review for futility of the trial in the context of lack of adequate recruitment.

5.c Definitions of Adverse Events

Severe adverse events: pelvic infection (endometritis, cervicitis or pelvic inflammatory disease) as diagnosed by cervical culture and physical exam, spontaneous miscarriage (pregnancy loss prior to 20 weeks gestation) or increased contamination rates in the lab which is routinely monitored for by our embryologists.

Non-severe adverse events include adverse effects of antibiotic administration including yeast vaginitis, abdominal pain, diarrhea, nausea and vomiting.

5.d Classification of Events

Reportable severe events include development of pelvic infection following embryo transfer, a significant increase in spontaneous miscarriage rates or a note in increased contamination rates in the lab. Risks of pelvic infection in this low risk population following embryo transfer approaches zero and we do not anticipate this occurring. We anticipate miscarriage rates to be equivalent or improved in the non-prophylaxis group but will be closely tracked for any increase in incidence. The lab uses gentamicin routinely in embryo culture media to decrease contamination rates and will continue to be closely monitored as is standard for quality control measures in our lab for any increase in contamination rates.

Reportable non-severe adverse events include yeast vaginitis, nausea and vomiting or other adverse reactions from antibiotic prophylaxis which the patients will report to their nurses.

5.e Data Collection Procedures for Adverse Events

In addition to principle investigator review of adverse events, a data and safety monitoring board (DSMB) will be established. This will include [name], [name], [name] and [name] and [name], MSCI. The designated group will meet once enrollment reaches 50% and then every 6 months thereafter. Adverse events will be noted in the patients chart and in the redcap database for complete capture and tracking. Data will be analyzed if a noted increase in severe adverse events is noted or otherwise once enrollment reaches 50% and then every 6 months thereafter when the DSMB meets.

5.f Reporting Procedures

Patients will be instructed to report any adverse symptoms to their respective nurse or doctor. These events will be immediately reported to the PI or research project coordinator.

5.g Adverse Event Reporting Period

Until study completion.

-

F Statistical Plan

F1 Sample Size Determination and Power

Given the conflicting evidence toward benefit of routine antibiotic prophylaxis and IVF outcomes, a non-inferiority approach was selected to test our hypothesis that no prophylaxis is not inferior to routine antibiotic administration. A total sample size of 356 patients (178 per arm) was determined based on an average baseline clinical pregnancy rate of 41% within our practice in this population with a non-inferiority margin of 15%, 80% power, and using a one sided $\alpha=0.025$ while estimating a 5% drop out rate. Our practice completed approximately 500 fresh IVF cycles in 2016. Our exclusion criteria are broad and we do not anticipate patient recruitment to be difficult. We believe 356 patients is feasible and estimate a 14 month timeline to complete recruitment if we enroll 7 patients at minimum per week.

F2 Interim Monitoring and Early Stopping

Interim analysis will be performed according to the Haybittle-Peto approach at 50% enrollment and 75% enrollment. This study will be considered safe to continue if there is an absence in trend toward severe adverse maternal, pregnancy or laboratory outcomes in either group. The DSMB will also assess recruitment progress and will review for futility of the trial in the context of lack of adequate recruitment. Data will be formally analyzed at 50% enrollment and then every 6 months thereafter to assess for early termination of the study.

F3 Analysis Plan

See Table 1 for timetable of patient enrollment and analysis. Our practice is required to track patient demographic data and cycle outcome measures to report to the Society for Assisted Reproductive Technology. Data are recorded and tracked through Research Electronic Data Capture (REDCap). Data from enrolled patients will be exported and tracked in a separate secure REDCap dataset from our existing dataset. All of our outcome measures are routinely tracked, and no additional data query will be required to address potential confounders as listed in Table 2.

F4 Statistical Methods

Intention-to-treat and per protocol analyses will be performed. Chi-squared and Fisher's exact tests will be used to compare categorical variables as appropriate. Kolmogorov-Smirnov test will be initially used to assess the distribution pattern of continuous variables. Normally distributed variables will be analyzed via Student's t-test. Non-normally distributed continuous variables will be analyzed with the Mann-Whitney U test. The primary analysis is based on difference in clinical pregnancy rate between the two groups. The sample size estimation for the study is based on this comparison with a non-inferiority approach as described above with an absolute difference of 15% or less to be considered non-inferior. Secondary analyses will include spontaneous miscarriage rate and embryo development. A subsequent interval analysis will assess live birth rate. Pearson's correlation coefficients will be used to quantify the association

between the two groups and embryo development. $P < 0.05$ will be considered statistically significant.

Each microbiota sample will have the taxon indicated as relative abundance. To assess the diversity across an IVF cycle, after log transformation, linear mixed regression will be applied. Wilcoxon rank sum will be used to measure for difference in richness and diversity with clinical outcomes of clinical pregnancy rate, miscarriage rate and embryo outcomes.

IBM® SPSS® statistics version 23 will be used for all analyses.

F5 Missing Outcome Data

All outcome data is required to be tracked by SART and no additional query will be required. We do not anticipate any issues with missing outcome data.

G Data Handling and Record Keeping

G1 Confidentiality and Security

Our practice is required to track patient demographic data and cycle outcome measures to report to the Society for Assisted Reproductive Technology (SART). Data is currently recorded and tracked through Research Electronic Data Capture (REDCap). REDCap is a secure web-based application designed to support data capture for research studies, providing 1) an intuitive interface for validated data entry; 2) audit trails for tracking data manipulation and export procedures; 3) automated export procedures for seamless data downloads to common statistical packages; and 4) procedures for importing data from external sources.¹⁸ Enrolled patients will be exported and tracked in a separate REDCap data set from our existing dataset.

G2 Records Retention

Study records will be stored and tracked through REDCap as noted in G1. Signed consents will be kept in a locked cabinet in a locked office. Data will be retained until study enrollment and analysis is complete.

H Study Administration

H1 Organization and Participating Centers

Washington University Department of Reproductive Endocrinology and Infertility.

H2 Funding Source and Conflicts of Interest

The PI, [name] is a recipient of funding from NIH 5T32HD055172 as a part of her Masters of Science and Clinical Investigation clinical research track. There are no conflicts of interest to report.

H3 Subject Stipends or Payments

Not applicable.

H4 Study Timetable

See Table 1.

I Publication Plan

We plan on presenting our findings at national meetings including those for American Society for Reproductive Medicine and Society for Reproductive Investigations. We plan to publish our results in journals that have a high impact among reproductive endocrinologists within 6 months of completing our data collection.

J Attachments

J1 Tables

Figure 1: Timetable (months)

	1	2	3	4	5	6	7	8	9	10	11	12	13	14	15	16	17	18	19	
Patient Recruitment	X	X	X	X	X	X	X	X	X	X	X	X	X	X						
Analysis															X	X	X			
Manuscript Composition																	X	X	X	

Table 2. Potential confounders

Patient history	Cycle level factors	Cycle outcome
-----------------	---------------------	---------------

Demographic data: Maternal age, race, ethnicity Medical history: BMI, tobacco use Obstetric history: gravidity, parity Infertility diagnosis Duration of infertility Number of prior IVF cycles Baseline labs: Follicle stimulating hormone or antimullerian hormone level, antral follicle count	Total amount of gonadotropin administered Stimulation protocol Number oocytes collected Number mature oocytes Insemination method (conventional vs. intracyto-plasmic sperm injection [ICSI] vs. partial ICSI) Number oocytes normally fertilized (two pronuclei) Day of embryo transfer Number of embryos transferred Number of embryos frozen	Clinical pregnancy rate Spontaneous miscarriage rate Live birth rate
---	---	--

K References

1. www.sart.org
2. Czernobilsky B. Endometritis and infertility. *Fertil Steril.* 1978;30:119-130.

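### The only stated female virome swab is at embryo transfer, too late for fertilization or failure before transfer, and F4 does not say which microbiome swab goes with which outcome

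*Combined protocol and SAP*

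**What the plan says.** **Sampling in women.** Section A3 sets the microbiome swabs "at the time of baseline testing, prior to egg retrieval and at the time of embryo transfer". It then adds the virome: "Lastly we plan to obtain a swab at the time of embryo transfer to assess the human virome". The visit schedule for the microbiome/virome study (E4) lists no earlier virome swab and says of the last visit: "The third and final specimen will be obtained via midvaginal swab prior to embryo transfer". Its sentence on freezing does not say which swabs serve the virome. The catheter tip mentioned in D2 2.e is also a transfer-day specimen.

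**Sampling in men.** A3 says that part of the sample produced at the time of fertilization "will be obtained to evaluate the microbiome and virome in them in the same fashion". The E4 schedule puts it under the embryo transfer visit: "When the male partner produces a sample for use for IVF at this time, a 100 microliter volume will be obtained and frozen separately".

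**Hypothesis and analysis.** Specific Aim 5 (C2) expects that "subclinical eukaryotic viruses will be associated with negative IVF cycle outcomes". A3 says the findings will be correlated with the clinical outcomes tracked for the main trial. F4 plans a Wilcoxon rank sum test of "difference in richness and diversity with clinical outcomes of clinical pregnancy rate, miscarriage rate and embryo outcomes". It names no swab, change score or summary across swabs, and it contains no virome analysis.

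**Women without transfer.** D2 2.f expects that some women will not reach retrieval or "may not get an embryo transfer due to either a poor response to medications or poor embryo quality". It counts them in the 5% drop-out and leaves them out of the analysis.

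**The concern.** An association between a specimen and an outcome is hard to interpret when the specimen is taken after the outcome, and harder still when it is missing because of the outcome. Both apply to the female virome if it is related to embryo development or to failure before transfer. Fertilization is settled before the transfer-day swab, and the women with the poorest response or embryos never have that swab, although theirs are among the most negative cycle outcomes that Aim 5 could cover.

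For the microbiome the problem is an open choice. A rank sum test needs one value per woman, and F4 leaves open which of three swabs supplies it. The transfer swab could be used for outcomes that came before it, or the swab could be chosen after results are seen. The exclusion in 2.f would also remove women with poor embryos from the embryo-outcome analyses even where their baseline and pre-retrieval swabs are in the freezer.

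At stake is what the exploratory study can claim. The main non-inferiority comparison is not touched.

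**Working it through.** **1. The plan's own figure.** The one sample size with a stated basis is that of the main trial (F1): 41% clinical pregnancy in both arms, margin 15 points, one-sided alpha 0.025, power 80%, drop-out 5%.
- Per arm: (1.96 + 0.8416)² × 2 × 0.41 × 0.59 / 0.15² = 7.849 × 0.4838 / 0.0225 = 168.8, so 169.
- With drop-out: 169 / 0.95 = 177.9, so 178 per arm and 356 in total. This reproduces the plan.
- The 50 couples of the exploratory study have no stated calculation. Nothing below depends on the 356.

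**2. Order of specimens and outcomes in women**

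| Outcome | Baseline swab | Pre-retrieval swab | Transfer swab (the only stated virome swab) |
|---|---|---|---|
| Fertilization rate | before | before | after |
| Blastocyst conversion and utilization | before | before | mostly after |
| Reaching transfer | before | before (women who reach retrieval) | exists only if transfer is reached |
| Clinical pregnancy, miscarriage, live birth | before | before | before |

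The entry is *mostly after* because Table 2 records day of transfer as a variable, and a blastocyst result could follow an early transfer. Even then the remaining embryos were in culture, not in the woman, when the swab was taken.

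**3. Women with no female virome value.** Inputs: 50 women (A3), 41% clinical pregnancy and 5% drop-out (F1). The 5% covers all drop-out, so using it for failure to reach transfer is an approximation. The 10% and 20% rows are assumptions that the documents do not give.
- Women without clinical pregnancy, if 41% is per woman enrolled: 50 × (1 − 0.41) = 29.5.
- F1 gives no denominator for the 41%. If it is per transfer, the non-pregnant number at 5% is 50 − 0.41 × 47.5 = 30.5; at 10%, 50 − 0.41 × 45 = 31.6; at 20%, 50 − 0.41 × 40 = 33.6.

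| No transfer | Women without swab | Share of non-pregnant, 41% per woman | Share, 41% per transfer |
|---|---|---|---|
| 5% (plan) | 2.5 | 2.5/29.5 = 8% | 2.5/30.5 = 8% |
| 10% (assumed) | 5 | 5/29.5 = 17% | 5/31.6 = 16% |
| 20% (assumed) | 10 | 10/29.5 = 34% | 10/33.6 = 30% |

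**4. The semen aliquot.** On A3's timing, a male/female couple that reaches fertilization but not transfer has a male virome value. On E4's timing, under the transfer visit, it may not. The two sections must be reconciled. On either timing, a couple that stops before retrieval has none.

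**The case against.** - **F4 does link the microbiome to outcomes.** This stands. A reader might infer that embryo outcomes will be related to later microbiome swabs, but the plan does not say so. Two of the three swabs precede fertilization; only the choice of swab is missing.
- **No virome-to-embryo test is specified.** F4 has no virome analysis, and the cycle-outcome column of Table 2 lists only clinical pregnancy, miscarriage and live birth. On that reading the transfer swab precedes every Aim 5 outcome. This is a fair reading, but not the only one: D1 makes embryo development a secondary outcome, F4 counts embryo outcomes among clinical outcomes, and A3 promises correlation with the tracked outcomes. The plan has to say which reading applies.
- **Couples without transfer may still have a virome value.** This stands for the male specimen, subject to the conflict over its timing. The gap concerns the woman's specimen.
- **Selection on transfer need not weaken an association.** This also stands. If viruses act on implantation, leaving out women who failed for other reasons could sharpen the signal; if they act before transfer, signal is lost. The documents do not settle the direction.
- **The exclusion is declared, and association given transfer is a legitimate target.** True, but Aim 5 is not worded as conditional. Declaring the exclusion does not remove the selection from the embryo-outcome analyses, and it sits uneasily with F4's intention-to-treat analysis.
- **This is an exploratory pilot.** Agreed. That limits the weight of the point, but the main correction is almost free.

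**Conclusion.** The point holds for the female virome, and for the microbiome only as an unspecified choice of swab. Followed as written, the female virome postdates fertilization and most embryo culture and is absent for women who fail before transfer. It cannot address Aim 5 for those outcomes. For clinical pregnancy, miscarriage and live birth among women transferred, its timing is sound.

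The size that rests on the plan's figures is small: about 2.5 of 50 women, about 8% of those without clinical pregnancy. This treats the whole 5% drop-out as failure to reach transfer. Larger shares rest on assumed rates. The likely direction of bias cannot be stated. The stronger conclusion, that the plan builds reversed timing into the microbiome analysis or leaves every failing couple without virome data, is not supported.

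The change is worth making before the frozen specimens are batch analyzed. It does not affect the primary analysis or the 356.

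**What to change.** 1. In F4, name the swab for each outcome. Use the pre-retrieval swab for fertilization rate, blastocyst rates and reaching transfer, with the baseline swab as sensitivity analysis. Women who stop before retrieval can contribute only through the baseline swab, so that analysis should include them for reaching transfer.
2. Keep women without transfer in those analyses, stated as an exception to D2 2.f.
3. Restrict transfer-day microbiome and virome analyses to clinical pregnancy, miscarriage and live birth among women transferred. Write the virome analysis and its population into F4, and word Aim 5 as conditional on transfer.
4. Reconcile A3 and E4 on when the semen aliquot is taken.
5. Optionally, sequence the virome in the stored pre-retrieval swab as well.

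**Cost.** Items 1 to 4 need only text: no new swab, visit or assay. The price is a narrower Aim 5 claim. Item 5 would add up to 50 sequencing runs and depends on enough specimen remaining, which the documents do not establish. Replacing the transfer swab, rather than adding to it, would give up the virome specimen nearest implantation.
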